# **Balancing and Covariate Adjustment Methods**

The analysis will utilize inverse probability of treatment weighting (IPTW) to adjust for differences in the baseline characteristics between the PCV13 vaccinated and PCV13 unvaccinated cohorts. IPTW creates a pseudo-population in which the distribution of measured baseline covariates is independent of treatment assignment, thereby mimicking randomization.

Propensity scores (PS) will be created using a logistic regression model and used to calculate the inverse probability of treatment weights. Standardized mean differences (SMD) will be used to assess covariate balance before and after weighting. An absolute standardized difference less than or equal to

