#### PFIZER CONFIDENTIAL

CT24-WI-GL02-RF02 6.0 Non-Interventional Study Protocol Template For Secondary Data Collection Study Page 35 of 53 0.1 will be considered as balanced. Stabilized weights will be used to limit the impact of outliers and truncation at the 1st and 99th percentiles may be considered. Covariates with residual imbalance after weighting will be included in the final models for further adjustment to control for potential confounders. Depending on the balance checks for censoring status within the IPTW-weighted population, IPTW may be combined with inverse probability of censoring weighting (IPCW) to address potential issues of informative censoring. IPCW adjusts for potential biases due to censoring, with weights calculated based on the probability of censoring at various time points.

Only baseline covariates will be adjusted for using IPTW. Time-varying influenza vaccination status will be adjusted for directly in the Cox proportional hazards models for the primary outcomes analysis. Individuals will be classified as vaccinated starting 15 days after their first claim for an influenza vaccine during each respiratory season and considered vaccinated until the end of that respiratory season. The Cox model will treat influenza vaccination as a time-varying variable using a counting process. Baseline covariates included in the PS models for IPTW and IPCW will be finalized based on their clinical and statistical importance and will be detailed in the SAP.

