### **Mediation** Analysis

The study will also include a secondary analysis to examine mediation. The mediation analysis will estimate the direct and indirect effects of PCV13 receipt on MACE, examining the extent to which the relationship between PCV13 and MACE within 1 year of follow-up is mediated by CAP. Direct (c') and indirect effects (a\*b) will be estimated. This analysis will employ the product method, which

PFIZER CONFIDENTIAL

CT24-WI-GL02-RF02 6.0 Non-Interventional Study Protocol Template For Secondary Data Collection Study Page 36 of 53 uses a logistic weighted mediation model to assess the mediator and a Cox model weighted outcome model to derive the HR and confidence intervals. Additionally, a counterfactual-based mediation analysis may be considered. This approach utilizes simulations to estimate the Controlled Direct Effect (CDE) and the Natural Indirect Effect (NIE), providing a comprehensive understanding of the mediation process. The mediation analysis will only adjust for influenza vaccination status during baseline. Further details on the mediation analysis will be provided in the SAP.

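### The mediation weights balance PCV13 groups, not CAP status, so common causes of CAP and MACE are left uncontrolled and the indirect effect may be biased

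*Protocol*

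**What the plan says.** Protocol 9.7, Mediation Analysis, states of the 1-year analysis for secondary objective 4: "This analysis will employ the product method". The direct effect is c' and the indirect effect is a*b. The method "uses a logistic weighted mediation model to assess the mediator and a Cox model weighted outcome model to derive the HR and confidence intervals". The same paragraph adds that "a counterfactual-based mediation analysis may be considered", that "The mediation analysis will only adjust for influenza vaccination status during baseline", and that "Further details on the mediation analysis will be provided in the SAP".

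The weights are described under Balancing and Covariate Adjustment Methods. They create a pseudo-population in which the "distribution of measured baseline covariates is independent of treatment assignment". Balance is judged by standardized mean difference (SMD), with 0.1 or less counted as balanced. "Only baseline covariates will be adjusted for using IPTW", and "Covariates with residual imbalance after weighting will be included in the final models for further adjustment to control for potential confounders".

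Table 3 codes CAP as none versus at least one event between the start of follow-up and the minimum date of censoring. Table 4 lists the outcome under study among the censoring variables.

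**The concern.** Treatment here means PCV13. Weights that make covariates independent of PCV13 support the PCV13-to-CAP path (a) and the total effect. They do nothing to make segments with CAP comparable to segments without it, and that comparison is what the CAP coefficient b in the MACE model needs. Age, COPD, outpatient heart failure, dementia and functional status are all in Table 5 and are plausible causes of both CAP and MACE.

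The residual-imbalance rule does not help, because it looks at the PCV13 contrast. The better the weighting works, the fewer covariates the rule passes into the outcome model. The error in b carries straight into a*b and any proportion mediated, and it shifts the direct effect, even with perfect balance by PCV13.

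**Working it through.** The protocol gives no figure for the mediation analysis, so there is nothing to reproduce. The check has two parts.

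**1. Closed form, CAP treated as fixed at baseline.** For a binary confounder X that multiplies the MACE hazard by h, the apparent CAP hazard ratio is approximately

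HR_obs = HR_true × [1 + (h−1)·P(X|CAP)] / [1 + (h−1)·P(X|no CAP)].

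All inputs are assumptions: X prevalence 20%; 1-year CAP risk 2% without X and 4% or 6% with X; h of 2 or 2.5.

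- CAP 2% vs 6%, h = 2.5: P(X|CAP) = 0.012/0.028 = 0.429 and P(X|no CAP) = 0.188/0.972 = 0.193. The factor is 1.643/1.290 = 1.273. A true 1.5 appears as 1.91 (log HR ×1.60) and a true 2 as 2.55 (×1.35).
- CAP 2% vs 4%, h = 2: P(X|CAP) = 0.008/0.024 = 0.333 and P(X|no CAP) = 0.192/0.976 = 0.197. The factor is 1.333/1.197 = 1.114. A true 1.5 appears as 1.67 (×1.27) and a true 2 as 2.23 (×1.16).

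**2. Simulation of the weighted models.** One run of 600,000 segments per scenario, one year of follow-up, no death or other censoring.

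Inputs based on the protocol: about 39.6% vaccinated and a MACE hazard of 0.0507 per year (9.5); CAP rate 0.0217 per year, the midpoint of 847 to 3500 per 100,000 (section 7, hospitalized CAP only).

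Assumed inputs: confounder prevalence 20%; vaccination probability 35% with the confounder and 41% without; true CAP hazard ratio 2.0; PCV13-CAP rate ratio 0.85; no direct PCV13 effect. Stabilized weights were estimated on the confounder, then a weighted logistic model for CAP and a weighted Cox model for MACE were fitted.

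CAP fixed at the start of follow-up (SMD by PCV13 after weighting was 0.00 throughout):

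| Confounder effect on CAP, MACE | SMD by CAP | CAP HR, weights only | CAP HR, confounder added | a*b, weights only | a*b, confounder added | Ratio |
|---|---|---|---|---|---|---|
| none | −0.01 | 1.98 | 1.98 | −0.1233 | −0.1233 | 1.00 |
| ×1.5, ×1.5 | 0.18 | 2.04 | 1.97 | −0.1193 | −0.1137 | 1.05 |
| ×2, ×2 | 0.31 | 2.19 | 1.98 | −0.1572 | −0.1372 | 1.15 |
| ×3, ×3 | 0.51 | 2.60 | 1.98 | −0.1620 | −0.1156 | 1.40 |
| ×3, ×0.67 | 0.52 | 1.93 | 2.11 | −0.1131 | −0.1288 | 0.88 |

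The confounder is perfectly balanced by PCV13, so the residual-imbalance rule would not select it. Between CAP groups it exceeds the protocol's own 0.1 limit in every confounded scenario.

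CAP as ever/never during follow-up (Table 3), and as a time-updated variable:

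| Confounder effect on CAP, MACE | Ever/never HR, weights only | Ever/never HR, confounder added | a*b, weights only | a × ln 2 | Time-updated HR, weights only | Time-updated HR, confounder added |
|---|---|---|---|---|---|---|
| none | 0.91 | 0.91 | +0.0175 | −0.133 | 1.85 | 1.85 |
| ×1.5, ×1.5 | 1.03 | 1.00 | −0.0054 | −0.128 | 2.10 | 2.03 |
| ×2, ×2 | 1.08 | 0.97 | −0.0121 | −0.107 | 2.20 | 1.98 |
| ×3, ×3 | 1.32 | 0.99 | −0.0431 | −0.107 | 2.72 | 2.04 |
| ×3, ×0.67 | 0.89 | 0.97 | +0.0185 | −0.113 | 1.82 | 1.99 |

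Under the ever/never coding a segment must stay free of MACE until CAP occurs to count as CAP-positive. That immortal time pulls b down and outweighed the confounding in every scenario. Time-updating CAP removes it, but the weights-only column then shows the confounding again (2.72 against 2.04 in the strongest case).

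At CAP rates of 0.00847 and 0.035 (effects ×2, ×2), the ever/never weights-only HR was 1.05 and 1.10, and the time-updated HR with the confounder was 1.88 and 2.03. Single runs carry noise. In the unconfounded case, roughly 600,000 × 0.0204 CAP events, half a year each at a hazard near 0.10, gives about 600 MACE events after CAP. The standard error of the log HR is then about 0.04, so 1.85 lies about two standard errors below 2.0.

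**The case against.** **SAP territory.** The protocol leaves further mediation details to the SAP, which is not shown, and regressors in a secondary model are commonly fixed there. That stands as far as a missing covariate list goes, and a missing list is not the point. The protocol itself fixes the weighted form of both models, and its one stated route for covariates into the final models checks the wrong contrast for b. A SAP that follows this text inherits the problem.

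**The text does not exclude covariates.** This is correct. A reader might infer that only imbalanced covariates may enter, or that baseline influenza vaccination is the sole adjustment. The documents support neither. The imbalance rule does not say that nothing else may enter. The influenza sentence is explained by the influenza row of Table 5, which contrasts baseline with time-varying status, so it concerns the timing of that one covariate. Nor does the protocol say outright that the mediation weights are the treatment weights, though that is the natural reading.

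**The direction is not certain.** A reader might infer that the indirect effect will be overstated. That does not hold. It needs confounders that raise both CAP and MACE and no opposing bias, and Tables 3 and 4 together create an opposing bias. Under that coding, adding the confounder moved the CAP HR to 0.97 to 1.00 when it raised both events, further from 2.0 than weights alone. Covariate adjustment without time-updating is therefore not a cure.

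**The exclusions narrow shared risk.** Section 9.2.2 removes high-risk conditions, recent hospital pneumonia and recent MACE. This may reduce the size, but age, COPD, outpatient heart failure, dementia, smoking and functional status remain as Table 5 covariates.

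**Other safeguards.** The negative control outcomes probe PCV13-outcome confounding. The CAP sensitivity analysis changes only the care setting. The counterfactual analysis is optional and needs the same confounders controlled.

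**Conclusion.** The concern holds in this form: as written, the mediation analysis does not control measured common causes of CAP and MACE on the CAP-to-MACE path, so the indirect effect and any proportion mediated may be biased. If shared risk factors raise both events, the bias from this source is upward. It was about 5% to 40% of a*b in the simulated cases with CAP fixed at the start, and 16% to 60% of the log CAP hazard ratio in the closed form. All of these sizes rest on assumed confounder prevalence and effects, and both calculations treat CAP as fixed, which Table 3 does not. With the ever/never variable the net bias was towards no mediation or a reversed sign, so the overall direction cannot be stated in advance. The primary analysis of MACE is not affected.

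**What to change.** In the mediation outcome model, include a prespecified set of baseline CAP-MACE confounders from Table 5 as regressors, regardless of their SMD by PCV13. Leave out prior respiratory failure, which Table 5 keeps as descriptive only. Inverse-probability weights for the mediator are an alternative. In addition, enter CAP as a time-updated variable, because covariate adjustment alone does not correct b under the ever/never definition. The SAP should then state how the CAP model and the time-updated coefficient are combined into the indirect effect.

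The cost is some extra model-building and analysis work. The covariates and event dates are already in the claims data, and with about 25 million adults estimated to be eligible the added parameters are not a burden.

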### 7. RATIONALE AND BACKGROUND

Community-acquired pneumonia (CAP) is a major cause of morbidity and mortality in older adults. A systematic review conducted in 2020 reported that in the United States (US), the estimated annual incidence of hospitalized CAP among adults aged  $\geq 65$  years ranges from 847 to 3500 per 100,000 persons. In a prospective study of adults hospitalized with CAP conducted in Louisville, Kentucky during 2014 to 2016, 6.5% of patients died during hospitalization, and mortality increased to 30.6% at 1 year after hospitalization. CAP can be caused by a wide range of viral, bacterial, and fungal pathogens, with Streptococcus pneumoniae typically reported as a leading bacterial cause. In the Etiology of Pneumonia in the Community (EPIC) study conducted by the US Centers for Disease Control and Prevention (CDC) at 5 hospitals during 2010-2012, S. pneumoniae was the most common bacteria identified and the third most common pathogen overall, behind rhinovirus and influenza virus. A systematic literature review published in 2020 that included 146 studies evaluating CAP etiology in adults in developed countries found that S. pneumoniae remains the most common bacterial cause of CAP, despite some declines in incidence in recent years. Detection of pneumococcal CAP is underestimated using traditional diagnostic methods such as sputum culture, as evidenced by the EPIC study, which found that use of serotype-specific urinary antigen detection (ssUAD) assay that detects the serotypes included in the 13-valent pneumococcal conjugate vaccine (PCV13) substantially increased detection of pneumococcal pneumonia. The Louisville, Kentucky adult CAP study conducted ssUAD testing for 24 pneumococcal serotypes and found that 13% of patients had pneumococcal pneumonia. They estimated that each year in the United States, more than 225,000 adults are hospitalized for pneumococcal CAP, and one quarter of these patients die within one year after hospitalization.

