Cardiovascular complications are common during and after CAP, with up to 30% of hospitalized CAP patients experiencing a major adverse cardiovascular event (MACE). Cardiovascular complications during and after CAP are closely associated with poor outcomes including mortality. Several pathophysiological mechanisms may contribute to the association between CAP and MACE outcomes, such as systemic inflammation resulting from pneumonia, or disruption of a previously stable plaque leading to an acute myocardial infarction. Additionally, there is evidence that the pathogens causing pneumonia, including *S. pneumoniae* in particular, can directly damage the cardiovascular system. Adult patients with pneumococcal CAP are at substantial risk for MACE. MACE outcomes are also common in adults with invasive pneumococcal disease. In a cohort of Dutch adults aged  $\geq$ 45 years, 4.2% experienced a cardiovascular event within one year after hospitalization for invasive pneumococcal disease, with acute coronary syndromes primarily occurring within 12 days of admission. Evidence from in vitro and animal studies has implicated the pneumococcal toxin pneumolysin in cardiac injury. In a non-human primate model of severe

PFIZER CONFIDENTIAL

CT24-WI-GL02-RF02 6.0 Non-Interventional Study Protocol Template For Secondary Data Collection Study Page 14 of 53 pneumococcal pneumonia, examination of cardiac tissue showed that *S. pneumoniae* invaded the myocardium and induced cardiac injury with necroptosis and apoptosis, and cardiac scarring occurred after antibiotic treatment. Studies in mouse models have determined that heart damage varies by pneumococcal strain. Similarly, clinical studies have revealed that MACE in patients with invasive pneumococcal disease are serotype dependent.

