# 9.3.3. Mediation

### Table 3.Mediation Variables

Variable	Role	Operational definition	Measurement period
Community-acquired pneumonia (CAP)	Mediator	
 
≥1 ICD-9-CM or ICD-10-CM diagnosis code for CAP in any setting, where there were no hospital admissions or ventilator use within the 30 days prior.
 
CAP with be categorized as having 0 or ≥1 CAP event. Individuals will be classified as having ≥1 CAP event if there is at least one diagnosis code for CAP during one of the following time segments:
 
1. ≥0 days after the unvaccinated index date and before the minimum date of censoring for the unvaccinated time segment
 
2. ≥14 days after the vaccinated index date and before the minimum date of censoring for the vaccinated time segment.
 
ICD-9-CM and ICD-10-CM codes are listed in Annex 1.
 
	Follow-up
Community-acquired pneumonia (CAP) sensitivity	Mediator	
 
≥1 ICD-9-CM or ICD-10-CM diagnosis code for CAP in the hospital setting, where there were no hospitalizations or ventilator use in the 30 days prior the hospital admission associated with the CAP diagnosis.
 
For individuals with multiple CAP diagnosis codes during the 1-year follow-up period, CAP will be classified as the highest level of care associated with a CAP diagnosis code.
 
CAP with be categorized as having 0 or ≥1 CAP event. Individuals will be classified as having ≥1 CAP event if there is at least one diagnosis code for
 
	Follow-up

PFIZER CONFIDENTIAL

CT24-WI-GL02-RF02 6.0 Non-Interventional Study Protocol Template For Secondary Data Collection Study Page 25 of 53

CAP during one of the following time segments:

 
≥0 days after the unvaccinated index date and before the minimum date of censoring for the unvaccinated time segment
 

 
4. ≥14 days after the vaccinated index date and before the minimum date of censoring for the vaccinated time segment.
 

ICD-9-CM and ICD-10-CM codes are listed in Annex 1.

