## 9.5. Study Size

To determine the appropriate sample size for our study, we conducted a power analysis based on logrank test. The analysis was designed to evaluate the effect of PCV13 vaccination on the risk of first event MACE, with the following key assumptions:

- Treatment-to-control group allocation ratio: Based on the feasibility study using data from September 14, 2014, to December 31, 2019, the proportion of the vaccinated group is 39.6%. Consequently, the treatment-to-control group allocation ratio was set to 2:3.
- Hazard ratio (HR): We assumed a hazard ratio of 0.85 for the vaccinated group compared to the unvaccinated group, indicating a 15% reduction in the risk of first event MACE associated with PCV13 vaccination. Another scenario with an HR of 0.8 is also provided.
- Hazard rate for control group: Based on the above feasibility study, the 5-year overall event probability was 21.2%. Consequently, we calculated the hazard rate for the control group to be 0.0507. This calculation was derived from the pre-assumed HR of 0.85, the overall 5-year survival probability, and the treatment-to-control group allocation ratio. For the scenario with HR=0.8, the corresponding hazard rate for the control group is 0.0518.
- Follow-up time: In this study, not all patients will complete the full duration of follow-up due to censoring events such as vaccination status switching or death. To account for this in the sample size calculation, we adjusted the calculation using shorter average follow-up periods. Specifically, we considered four follow-up durations: 1-year, 0.75 year, 3 years, and 2.75 years.
- Statistical power: 80%.
- Test was two-sided with significance level (α): 0.05, which corresponds to a 5% chance of a Type I error.

The required total sample sizes for each scenario were determined as follows to achieve a 80% power:

Hazard Ratio	Control Group Hazard Rate	Follow-up time in	Total N Required
		years	
0.85	0.0507	1	27,520
		0.75	36,485
		3	9,600
		2.25	12,585

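### The mediation plan for secondary objective 4 has no stated place for a PCV13-by-CAP interaction, and the CDE and NIE it names need not add up to the total effect

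*Protocol*

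**What the plan says.** Protocol Section 9.7, Mediation Analysis, commits to the product method: a weighted logistic model for CAP, a weighted Cox model for MACE, and from these a direct effect c' and an indirect effect a*b within one year. It then says that a counterfactual analysis may be considered, and describes it so: "This approach utilizes simulations to estimate the Controlled Direct Effect (CDE) and the Natural Indirect Effect (NIE), providing a comprehensive understanding". The section mentions no exposure-by-mediator term. It does not mention the natural direct effect, and the abbreviation list in Section 2 has CDE and NIE only. It does not say at which CAP level the CDE is evaluated. Further detail is left to the SAP.

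The mediator in Table 3 is all-cause and binary: "CAP with be categorized as having 0 or ≥1 CAP event".

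Section 7 gives the biology. PCV13 protects against vaccine-type pneumococcal CAP, and S. pneumoniae in particular is said to be able to damage the cardiovascular system directly. It adds that "clinical studies have revealed that MACE in patients with invasive pneumococcal disease are serotype dependent". On frequency, the Louisville study of hospitalized CAP "found that 13% of patients had pneumococcal pneumonia". The same section also gives the mechanism under study as fewer pneumonias of any cause.

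**The concern.** The product a*b uses a single b, so it treats a CAP episode as equally harmful in vaccinated and unvaccinated people. Section 7 gives a reason to doubt this. If PCV13 removes vaccine-type episodes selectively, the remaining CAP among vaccinees has a different mix. If vaccine-type CAP is also the more cardiotoxic kind, the remaining CAP is less harmful on average. PCV13 would then act through CAP in two ways: fewer episodes, and less harm per episode. A model with one b has no place for the second except c'.

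The optional counterfactual analysis as described does not repair this. With an interaction, the NIE is complemented by the natural direct effect and not by a controlled direct effect. The CDE also takes different values at CAP = 0 and CAP = 1.

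At stake is the answer to objective 4, the degree of mediation by CAP. A direct share produced by a change in CAP mix could be read as a non-pneumonia mechanism or as residual confounding.

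**Working it through.** **Plan's own figures.** The protocol gives no figure for the mediation analysis. The one borrowed here is the control hazard in Section 9.5. With a 5-year event probability of 21.2%, the assumption that "We assumed a hazard ratio of 0.85 for the vaccinated group compared to the unvaccinated group" and the fact that "the treatment-to-control group allocation ratio was set to 2:3", solving 0.6·exp(−5h) + 0.4·exp(−5·0.85·h) = 0.788 gives h = 0.0507, as stated. The sample size follows too. Freedman's formula needs 7.849 × (1 + 0.85·2/3)² / [(2/3)·0.15²] ≈ 1,284 events. The 1-year event probability is 0.0465, so N ≈ 27,600 against 27,520 in Table 6.

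**Inputs for the illustration**
- From the documents: 1-year MACE risk 1 − exp(−0.0507) = 4.94%; annual CAP incidence p0 = 0.847% to 3.5%; MACE risk after CAP 30% (stated as an upper figure); pneumococcal share of CAP 13%, used as the upper value of the vaccine-type share s0.
- Assumed: lower value of s0 5%; efficacy against vaccine-type CAP 45% to 75%; MACE risk ratio k for vaccine-type versus other CAP of 1, 1.5 or 2; no effect of PCV13 outside CAP, so the true non-CAP share is zero.

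**One case in full** (p0 = 3.5%, s0 = 13%, efficacy 75%, k = 2)
1. CAP risk in vaccinees: p1 = 0.035 × (1 − 0.13·0.75) = 0.03159.
2. Vaccine-type share of their CAP: 0.13·0.25/0.9025 = 0.0360.
3. MACE risk after other CAP: 0.30/(0.13·2 + 0.87) = 0.2655. MACE risk after CAP in vaccinees: 0.2655 × (1 + 0.0360) = 0.2750, against 0.30 in the unvaccinated.
4. MACE risk without CAP, both cohorts: (0.0494 − 0.035·0.30)/0.965 = 0.0403.
5. Total effect: 0.03159·(0.2750 − 0.0403) − 0.035·(0.30 − 0.0403) = −167.4 per 100,000.
6. NIE: (p1 − p0)·(0.2750 − 0.0403) = −80.1. Natural direct effect: p0·(0.2750 − 0.30) = −87.3. Their sum is −167.4, as it should be.
7. CDE at no CAP is 0, so CDE(0) + NIE = −80.1 and 87.3/167.4 = 52% of the effect is in neither. CDE at CAP is −2,495, so CDE(1) + NIE is 15.4 times the total effect.
8. Four-way: CDE(0) 0, reference interaction −87.3, mediated interaction +8.5, pure indirect effect −88.6; sum −167.4. Total effect minus CDE(0) is also −167.4, the whole effect.

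**Over the range of inputs**

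| k | CDE(0) + NIE leaves out | CDE(1) + NIE, as multiple of total effect |
|---|---|---|
| 1 | 0% | 1 |
| 1.5 | 32–37% | 10–44 |
| 2 | 47–54% | 15–64 |

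The percentages cover both forms of the NIE (total and pure).

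**The c' form.** A log-linear fit without interaction to the expected cell counts, standing in for the Cox model, assigns 0% of the log effect to the direct path at k = 1, 33–36% at k = 1.5 and 48–53% at k = 2. A separate calculation with the same kind of stand-in gave 37–40% and 52–56%. Both say about a third to a half.

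**Does the interaction term alone suffice?** No. With it, natural direct effect plus NIE equals the total effect, but step 6 shows the change-of-mix part still inside the natural direct effect. Only total effect minus CDE(0), or the four-way table, attributes it to CAP.

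**The case against.** The strongest reply is that model specification belongs in the SAP, and the protocol neither includes nor excludes an interaction. A reader might infer that the plan rules one out; it does not. Still, c' and a*b are stated estimands, and a single a*b holds only with a common b. The pairing of CDE with NIE is also written text.

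Second, the counterfactual step is only something that may be considered, so the pairing does not touch the product-method result, and the protocol nowhere claims that the two effects add up. That stands. It limits the pairing's reach but leaves the product form as the main answer, with no adequate alternative described.

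Third, a reader might infer from Section 7 that the CAP effect must differ between cohorts. The documents do not support that. The serotype statement compares patients within invasive pneumococcal disease, no document gives k, and the stated mechanism is a reduction in pneumonia of any cause. The interaction is plausible, not established.

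Fourth, the mediator is the occurrence of CAP. Under natural-effect definitions, less harm per episode properly belongs to the direct effect, and total effect minus CDE(0) is a different quantity, the portion eliminated. This is correct and is why the two should be labelled separately.

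Finally, the absolute amounts are small. In the case worked above, 87.3 per 100,000 is 1.8% of the 4.94% risk (87.3/4,940), against a planned 15% hazard reduction. Objective 4 asks about the share, however, so the split matters whatever the absolute size.

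**Conclusion.** The point holds in conditional form. As written, the plan has no stated way to represent a CAP effect that differs by vaccination status, and its optional pair of effects is not a decomposition when one exists. If vaccine-type CAP carries 1.5 to 2 times the MACE risk of other CAP, about a third to a half of a wholly CAP-mediated effect would be called direct or left out. At equal risk nothing is lost.

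These percentages are illustrations, not forecasts. They rest on assumed values of the risk ratio, efficacy and lower vaccine-type share, and on CAP inputs for hospitalized patients, whereas the main mediator counts CAP in any setting. It would go too far to say that the plan will understate mediation. The point concerns secondary objective 4 only and leaves the primary MACE hazard ratio unchanged. It should be settled before the mediation analysis is run.

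**What to change.** - Include a PCV13 × CAP term in the mediation outcome model, and report it.
- Pair the NIE with the natural direct effect, or report the four-way decomposition (CDE at no CAP, reference interaction, mediated interaction, pure indirect effect), on the 1-year risk scale so that the parts add up.
- State that the CDE is evaluated at no CAP.
- Report total effect minus CDE(no CAP) as the portion eliminated, labelled separately from the portion mediated.
- Bootstrap intervals by person, because Section 9.1 lets one individual contribute two time segments.

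The cost is one extra model term and a fuller output table from the same data. With about 25 million eligible adults, sample size is no obvious obstacle.
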